## 1.0 Objectives

**1.1 Aim 1: Modify care.coach, an existing inpatient bedside digital relational agent to enhance the well-being, safety, and outcomes of patients undergoing hematopoietic cell transplantation (HCT).** We will convene a focus group consisting of HCT nurse navigators, inpatient HCT nurses, and HCT physicians and extenders to determine appropriate modifications to the care.coach health coaching protocols and technology setup for the inpatient HCT setting, including development of educational modules that will be provided to patients undergoing HCT.

**1.2 Aim 2: Iteratively pilot the modified avatar agent in three cohorts of six patients each.** We will assess the feasibility of the patient education and relational functions of the digital avatar.

## 2.0 Background

**2.1** Among patients who undergo reduced intensity conditioning stem cell transplantation (RIC), relatively lengthy inpatient stays are routine for pre-HCT conditioning and receipt of donor cells. As those who receive this type of transplant tend to be older (60 to 75) and/or have baseline comorbidities, the inpatient stay can be difficult. Indeed, in-house delirium is one of the most frequent and distressing complications, even though it is typically a treatable, reversible syndrome.

The incidence of delirium in cancer patients undergoing myeloablative HCT is about 50%, and the presence of delirium at any point during hospitalization after transplantation has been shown to be highly predictive of mortality (odds ratio = 14). Also, the medications and side effects that accompany RIC HCT place this population at high risk for falls, and sustained low platelet counts following transplant exacerbate risk of death in the event of a fall. Many risk factors for falls among HCT patients correspond to risk factors for delirium and preventing delirium in cancer patients can also prevent falls. Moreover, HCT often experience stress, anxiety, anger, depression, insomnia and loneliness, with the percentage of depressed patients increasing more than two-fold after 2 weeks of isolation. Among HCT patients, research has shown that loneliness during hospital stay is negatively associated with overall quality of life six months after transplant, reducing both social and functional well-being, increasing difficulty of managing disease symptoms six months after transplant, and increasing ratio of neutrophil to monocyte counts 30 days after transplant (an indicator of poorer survival rate).

Inpatient non-pharmacological interventions that have been implemented to improve the quality of life (QOL) of pediatric and adult HCT patients include psychoeducational, exercise, and mindfulness interventions, all of which hold

**PROTOCOL TITLE:** *Development and Piloting of Avatar-based Intervention to Support Patients Undergoing Stem Cell Transplantation*

potential to outcomes during patients' hospital stay. In a multimodal study, individualized psychoeducation was provided to HCT patients 5 days a week alongside other interventions; patients showed an improvement for a variety of symptoms. Individualized and supervised exercises routines, such as daily dynamic exercises, stretching exercises, resistance training and progressive relaxation training, have been implemented and well received in both pediatric and adult HSCT settings. Mindfulness mediation (MM) practices can be easily provided to patients and have the potential to relieve patient distress. Although sleep interventions have been implemented in a wide variety of inpatient populations, they have not specifically been studied in the inpatient HCT population. Since different sleep interventions may better serve some populations more than others, it is unclear which sleep interventions may be the most beneficial to HSCT patients.

Indeed, a combination of psychoeducational, exercise, sleep, and mindfulness interventions could be applied in HCT patient settings simultaneously with the goal to improve patient QOL and to potentially improve patient outcomes. Moreover, for RIC HCT, post-HCT changes in lifestyle are complex, including nutrition, hydration, transplant medications, home disinfection, socialization, and others. For this population, the Health Belief Model, and Prochaska's Transtheoretical model of change would argue that patients who are hospitalized and waiting for their HCT to occur would be highly motivated to learn about these items being in the "groundwork for change/take action" phase while admitted.

care.coach™ provides a care support and health coaching platform in which a patient-facing interface is a digital relational agent, appearing on a tablet device as a dog or cat avatar to enable a non-judgmental, positive emotional connection for inpatients during their stay. Each avatar is controlled directly by a 24x7, world-wide team of trained humans known as "health advocates," who are background checked, psychometrically screened, and receive specialized training (non-medical). Each health advocate can cost-effectively monitor and engage 12 or more patients sequentially (2 simultaneously) through audio/visual feeds from the patient's device and send text commands which are converted into the avatar's voice through a speech synthesis engine. The health advocates are guided by a software-driven expert system embedded into their work interface, which implements evidence-based clinical protocols to support patient self-management and care coordination.

Pace University conducted a clinical pilot of the care.coach technology in 2016 at Jamaica Hospital Medical Center with 95 hospitalized (medical/surgical) older adults at high falls or delirium risk. Mean age was 76.5 years, with 55% female, 46% African-American, and 44% speaking English as a second language. Typical length of stay was 3-6 days. On average, the avatars performed 71.3 observational check-ins, 61 minutes of

**PROTOCOL TITLE:** *Development and Piloting of Avatar-based Intervention to Support Patients Undergoing Stem Cell Transplantation*

engagement using 11.5 images or audio files, and 6.5 protocol-driven tasks per patient, per day, based on certain protocols derived from the Hospital Elder Life Program (HELP). Compared to randomized control patients with a daily nurse student visit (n=54), intervention patients with our bedside avatar (n=41) showed a significantly greater reduction in delirium score (CAM, p=0.003) and loneliness (UCLA-LS, p=0.008). The primary intervention unit had 0.9 falls per 1000-patient days during the 3-month study period, compared to 6.5 on the control unit (86% reduction in fall rate). University of Washington has published 3 peer-reviewed papers about how the avatars help reduce loneliness, increase social support through informational, affectionate, and positive social interaction mechanisms, and decrease depressive symptoms among older adults in the community, including those with mild cognitive impairment. Quality improvement projects with care.coach health plan customers have also reported high patient and provider satisfaction, and reduced anxiety based on GAD-7 surveys.

In summary, digital conversational agents provided to patients offer potential benefits to patients including a reduction in delirium, and this technology has not been offered to patients in HCT settings. We propose to pilot this technology after modifying it to include educational protocols tailored to the needs of RIC HCT patients additionally offering education in post-HCT home care.

**2.2 Draft care.coach Clinical Protocols:** The following protocols will be developed into lessons that will be presented by the avatar.

[1] Diet & Hydration

- Hydration reminder, question
  - Importance of staying hydrated to maintain kidney health, drinking at least 2 liters of fluid per day with the goal of 2-3 liters per day ( aiming for non-caffeinated beverages)
- Meal rating, enjoyment
- Permitted outside foods (during inpatient transplant)
  - Beverages : canned sodas, juices, flavored drinks, nutritional supplements
  - Canned items: canned foods EXCEPT grapefruit, canned vegetables, canned soups and stews (portioned sized)
  - Cookies, crackers, and snacks : all individually portioned packages cookies, crackers, and chips, individually packaged pies and cakes that are commercial, shelf-stable products
  - Candy : individually wrapped hard candy and candy bars
  - Frozen entrees: Only frozen entrees that are individual portion-sized, remain frozen during transport to you, and have been cooked at BWH, either by room service or in the floor microwave

**PROTOCOL TITLE:** *Development and Piloting of Avatar-based Intervention to Support Patients Undergoing Stem Cell Transplantation*

- Inquiry about (healthy) eating habits/plans, fruits & vegetables (at home after transplant)
  - Vegetables: May eat fresh vegetables, raw or uncooked, as long as they are washed well EXCEPT FOR raw broccoli and cauliflower
  - Frozen vegetables: May eat frozen vegetables, raw or uncooked, as long as they have been washed well EXCEPT FOR broccoli and cauliflower which must be cooked and cannot be eaten raw
  - Canned vegetables: Can eat and do not have to be cleaned or cooked
  - Vegetable drinks : May eat if they are pasteurized
  - Fruits: Do not eat grapefruit or grapefruit juice, Seville oranges or marmalade made with Seville oranges
  - Fresh Fruits: can eat fresh fruits as long as they are washed well EXCEPT fresh berries (must be cooked completely). No cracks or bruises
  - Frozen fruits: May eat cooked or raw as long as they are washed well EXCEPT fresh berries (must be cooked completely). No cracks or bruises
  - Dried Fruits: May eat dried fruits
  - Canned Fruits: May eat, without washing or cooking
  - Fruit Cups: Can eat fruit cups packaged and pasteurized at the factory. You do not have to wash or cook fruit cups packed at the factory.
  - Fruit Drinks: Can drink fruit drinks if they are pasteurized
  - DO NOT EAT HONEY
- Food Safety (at home after transplant)
  - Reminder to check expiration dates before opening frozen or canned vegetables or vegetable juices
  - Vegetable cans, boxes, and bags should have no rips, dents
  - Wash bags, boxes, and cans before opening frozen or canned vegetables or vegetable juices
  - Clean the can opener before using it
  - Do not eat food prepared at friends' or family's houses. Do not eat out or eat takeout.
- Diabetes-related diet questions

[2] Physical Exercise [ambulation]

- Education about energy saving techniques, platelet precautions with activity and the overall importance of daily mobility to prevent fatigue/deconditioning
- Mobility assessment to determine levels (5) of ambulation, types of exercises (seated, standing, in bed)
- Otago exercises (home-based balance, strength exercises for older adults)
- Exercise arms, feet, hands, neck, hip, leg lifts, toe/calf raises

**PROTOCOL TITLE:** *Development and Piloting of Avatar-based Intervention to Support Patients Undergoing Stem Cell Transplantation*

- Inquiry about ambulation, going for a walk, exercise for the day

[3] Orientation/confusion/delirium

- Focused attention questions
- Confusion assessment (CAM) questions
- Orientation questions
- Cognitive impairment (MoCA) questions
- 5 senses countdown

[4] Non-pharmacological pain/anxiety management,

- Comfort level assessment/question(s)
- Evening meditation, guided imagery
- Simple breathing exercise, relaxation

[5] Sleep

- Encourage to go back to sleep if after 11PM

[6] Toileting/fall risk assessment

- Inquiry if need to use the bathroom (call nurse to assist if yes)
- Reminders – ambulatory device/assistive tech (cane, glasses, hearing aids), ask for assistance, do not rush, proper footwear, sleep in the center of the bed
- Falls check
- Tips for lowering your risk for falling
  - Wear non-skid socks or supportive footwear
  - Taking time with positional changes
  - Notifying staff if you have sudden onset of dizziness
  - Ensuring there is adequate lighting before getting up

[7] Psychosocial Support & Staff communication.

- Depression/mood question(s)
- Companionship/loneliness (FS/UCLA) question(s)
- Stress, worry, nervousness, anger question(s)
- “Fun facts”, patient education
- Establish urgent call criteria
- Interactive games
- Music, images, audiobooks

[8] HCT Medication Resources

- Tacrolimus
- Sirolimus
- Mycophenolate mofetil

**PROTOCOL TITLE:** *Development and Piloting of Avatar-based Intervention to Support Patients Undergoing Stem Cell Transplantation*

- Levofloxacin
- Acyclovir
- Atovaquone
- Bactrim
- Ursodiol

[9] Catheter Care

- Preparation to flushing catheter
  - Each lumen (small tube within your catheter) of central line catheter will need to be flushed once a day with 0.9% saline flush. The following steps can be used for either a PICC or a Hickman Central Line.
  - MUST wash hands prior, may choose not to wear gloves
- Steps to flushing catheter, which are as follows:
  1. Clean your worktable with a disinfectant wipe
  2. Gather supplies
    - a. Catheter caps
    - b. Alcohol wipes
    - c. Prefilled 10mL .9% saline flush
    - d. Gloves (optional)
    - e. Alcohol cover (Curos)
  3. Wash hands well with soap and water OR use an alcohol-based hand sanitizer
  4. Dry your hand with a clean paper towel
  5. If you have been taught to or want to use gloves, put them on now
  6. Take the flush syringe from the package
  7. Hold the syringe up in the air with the plunger pointing to the floor
  8. Tape the syringe so that any air bubbles rise to the top
  9. Take off the syringe cap
  10. Push the plunger to the 10mL mark. This will take out any air and extra flush from the syringe. Some flush may drop out.
  11. Hold the syringe upright and do not let the syringe touch anything
  12. Do you have a green alcohol cover over your catheter cap OR do you NOT have a green alcohol cover over your catheter cap
    - a. IF YES:
      - i. Remove the green alcohol cover only, do not reuse
      - ii. Leave the catheter cap in place
      - iii. Do not let the end of the catheter cap touch anything, including your body
    - b. IF NO
      - i. Open the alcohol wipe
      - ii. Scrub the catheter cap with the alcohol wipe for at least 10 seconds

**PROTOCOL TITLE:** *Development and Piloting of Avatar-based Intervention to Support Patients Undergoing Stem Cell Transplantation*

- iii. Let it dry completely
- iv. Do not let the end of the catheter cap touch anything, including your body after it has been cleaned

13. Hold the catheter cap
14. Put in and screw the flush syringe onto the end of the catheter cap
15. Open the clamp on the catheter
16. Flush the line with the saline using a push pause method. The turbulence helps to keep your line clear.
17. Firmly push 1cc then pause
18. Continue to push 1cc and pause until the line is flushed with al 10 ccs
  - a. If it is hard to push the flush, check to make sure the clamp is open. If it was clamped, open the clamp
  - b. If it is still hard to push, STOP. Do not push the flush. Close the clamp. Unscrew and remove the syringe. Call your doctor or Oncology Nurse Navigator.
19. Do not use force to flush
20. Be sure that the clamp is over wording “ clamp here”
21. Close the clamp on the catheter. You should hear a click.
22. Hold the catheter cap tightly and unscrew the syringe from the catheter. Be careful not to loosen the catheter cap from the catheter.
23. Always check to be sure the catheter cap is on tight
24. Put a new green alcohol cover over the catheter cap.
25. Now flush all other lumens of the catheter.
26. After you flush all of your lumens, throw your supplies away.

### **3.0 Inclusion and Exclusion Criteria**

#### *3.1 Aim 1: Screening and Eligibility*

We will convene one focus group with 8-10 participants who are DFCI/BWH HCT nurse navigators, inpatient HCT nurses, and HCT physicians and extenders (NP/PA).

#### **Eligibility for Aim 1:**

- Inclusion Criteria
  - Age 18+.
  - DFCI/HCC HCT nurse navigators, inpatient HCT nurses, and HCT physicians and extenders (NP/PA).

#### *3.2 Aim 2: Screening and Eligibility*

**PROTOCOL TITLE:** *Development and Piloting of Avatar-based Intervention to Support Patients Undergoing Stem Cell Transplantation*

Potential patients will be identified and screened through provider referral as identified in the transplant team's weekly (Friday afternoon) clinical meeting.

Screening and recruitment will be conducted by a trained research assistants (RA) who will utilize HIPAA-compliant and DFCI IRB approved patient approach procedures. Potential patients will be approached and consented upon inpatient admission for RIC HCT.

**Eligibility for Aim 2:**

- Inclusion Criteria:
  - Age 18+.
  - Admitted for reduced-intensity conditioning (RIC) allogeneic HCT (prior to day 0, generally day -7).
- Exclusion Criteria:
  - Deemed by clinical staff or RA to be unable to converse with an avatar, due to:
    - Severe, uncorrectable hearing impairment and simultaneous severe, uncorrectable vision impairment.
    - Severe speech impairment that precludes understanding by staff (and by extension, by the avatar).
    - Not fluent in English.

## **4.0 Study-Wide Number of Subjects**

Aim 1: This is a single-site study, located at Dana-Farber/BWH Cancer Center. We anticipate 8-10 participants for the focus group.

Aim 2: This is a single-site study, located at Dana-Farber/BWH Cancer Center. We anticipate enrolling 3 cohorts of 6 patients for a total of 18 participants.

## **5.0 Study-Wide Recruitment Methods**

Aim 1: Potential participants will be Dana-Farber/BWH Cancer Center staff. Department directories will be used to identify potential participants, who will be initially recruited by email and follow up contacts will be by phone and/or in person.

**PROTOCOL TITLE:** *Development and Piloting of Avatar-based Intervention to Support Patients Undergoing Stem Cell Transplantation*

*Aim 2:* All eligible patients as defined in Section 3.0 will be met by a trained RA soon after inpatient admission. This RA will be responsible for obtaining informed consent, as outlined in Section 23.0. All participants will be entered into the Clinical Trials Management System (CTMS) OnCore per DF/HCC guidance as per DF/HCC Policy REGIST-101.

## 6.0 Study Timelines

*Aim 1:* Prior to enrollment of the initial cohort of patients, we will convene a one-time 60minute focus group led by [name] PhD ([[name]\\[contact]](mailto:[contact])), a Senior Research Scientist in qualitative research, to discuss perspectives and opinions on implementing care.coach technology for HCT patients including education domains to include, frequency of avatar interactions, and anticipated staff concerns. This analysis will inform changes to be applied to the avatar, including script adjustments, prior to introducing the technology to patients in Aim 2.

*Aim 2:* We will complete the initial implementation of multiple HCT-related avatar changes across each of the categories in Section 2.2 and integrate them into an overall program schedule within 3 months. In the next 6 months, the HCT avatar program will then be piloted and iteratively improved through a phased, iterative user acceptance study with 3 consecutive cohorts of 6 RIC HCT patients each, receiving the avatar for up to 3 weeks per cohort (or patient discharge). After each cohort, user feedback will be gathered in the post-pilot survey (one week after disenrollment; see Appendix A), and protocol completion and patient-avatar engagement data will be analyzed.

## 7.0 Study Endpoints

7.1 *Aim 1:* Modifications to an avatar-based human-staffed artificial intelligence technology platform for use in an inpatient HCT setting, derived from thematic analyses of a focus group of DF/BWH Cancer Center HCT nurse navigators, inpatient HCT nurses, and HCT physicians and extenders (as described in Section 8.4)

7.2 *Aim 2:* PRIMARY: Retention rate in protocol from enrollment to hospital discharge or three weeks (whichever comes first). SECONDARY: Patient satisfaction rate with avatar in the final cohort; rate of completion of 80% of the HCT educational modules; rate of completion of post-pilot survey.

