## 8.0 Procedures Involved

### 8.1 Design/Study Type

**PROTOCOL TITLE:** *Development and Piloting of Avatar-based Intervention to Support Patients Undergoing Stem Cell Transplantation*

[figure not shown]
Aim 1: Focus group.

Aim 2: Single-arm feasibility pilot, with 3 cohorts of 6 patients (18 total).

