## 8.2 care.coach

care.coach is a “human-in the-loop” conversational agent (avatar) used to interact and converse with patients through natural dialogue and text-to-speech software that is powered by a team of trained human staff, called health advocates. A summary of the platform is shown in [Figure 1](#). Note that the Family Portal and Provider Portal depicted in this figure are features from the commercial care.coach device that will not be activated for the purposes of this study. These features provide patient-avatar interaction summaries to the providers and, if approved by the patient, to family members.

**Figure 1.** care.coach Avatar Platform

[figure not shown]
The care.coach patient-facing interface appears as a virtual animal avatar on a touch-screen handheld device. Patients interact with the avatar by speaking with it or tapping the avatar on the screen. This simple interface allows many users to be engaged effectively. The avatar has two states: awake and asleep. When the avatar is visually sleeping, the audiovisual (AV) stream is offline. To awaken the avatar on-demand, it must be tapped on the touchscreen device. When the avatar is visually awake, the care.coach staff-monitored AV stream will become active. Several times per day, the avatar will attempt to engage the patient spontaneously to provide key reminders, such as for hydration or activity, and initiate patient education modules.

If a patient participant is not available, does not respond, or the participant requests privacy, the avatar will go back to sleep. Whenever the avatar is visually awake, care.coach staff members monitor the AV streams from the avatar device to hear, see and interpret what users are saying and what is happening in the environment. This enables the care.coach staff to speak to study participants

**PROTOCOL TITLE:** *Development and Piloting of Avatar-based Intervention to Support Patients Undergoing Stem Cell Transplantation*

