## 9.0 Data and Specimen Banking

9.1 **Data Collected by care.coach:** Only meta-data will be collected through the avatar device. care.coach will be provided with a first-name, study-assigned patient number, and in-hospital location for safety functions, but will not be provided with other PHI. Upon completion of the study, name and in-hospital location data will be decoupled from other data and destroyed by care-coach. Audiovisual streams are recorded for immediate language processing and understanding but will not be stored post-processing. See Appendix C for care.coach security protocols.

9.2 **Data Collected by Dana-Farber:** No specimens will be collected or stored as part of this study. We will collect data on feasibility outcomes (retention, satisfaction, completion of modules) via post-pilot survey administered by the RA in person, at first follow up at Dana-Farber after discharge, or via telephone (Appendix A). Components of post-pilot survey questions on technology usability (Q1-19) were adapted from a published system usability scale. Questions on self-efficacy (Q20-28) were directly adapted from the General Self-Efficacy Scale. The remaining questions were newly developed for this study. Data will also be collected on patient demographics, transplant characteristics (type of transplant, donor characteristics, conditioning, GVHD prophylaxis, antibiotic prophylaxis, status of prior infectious diseases), and transplant outcomes (incidence and severity of GVHD, other infectious and non-infectious complications, relapse, survival). PHI will be stored with these data to allow for monitoring of long-term outcomes. Data will be stored on a secure server at DFCI up to 5 years from completion of the last study conducted as part of this project (dependent on whether we proceed to the Phase 2 study). One year after completion of the study, long-term analyses, and publication of deidentified findings, all PHI will be destroyed.

9.3 **Data Storage:** No specimens will be stored.

**9.4 Data Sharing:** Aggregated de-identified post-protocol survey data will be shared with care.coach; care.coach meta-data will not be shared with DFCI.

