
**PROTOCOL TITLE:** *Development and Piloting of Avatar-based Intervention to Support Patients Undergoing Stem Cell Transplantation*

findings from the focus group into the functions of the avatar to optimize the device functions for our patients.

**Aim 2:** We will enroll 18 patients in a single-arm pilot/feasibility study testing the care.coach avatar. The goal of the study is to determine if the avatar achieves the prespecified usability and feasibility outcome goals. As is common for HCT studies, the following covariates will be collected for each enrolled patient from hospital records and analyzed in conjunction with survey data collected by study RAs, with the support of the consulting biostatistician: incidence of delirium, falls, falls with injury, and sitter utilization, length of stay, use of benzodiazepines and sedatives, fluid “ins/outs” and meal fractions from nursing notes, in-hospital weights, neutrophil and platelet counts at fixed durations post-transplant, and incidence and severity of transplant-related complications including graft failure, graft-versus-host disease (GVHD), thrombotic microangiopathies (TMA), venous thrombosis, hemorrhage, acute infections and viral reactivations, idiopathic pneumonia syndromes, vaso-occlusive disease (VOD), cytokine release syndrome, mucositis, engraftment syndromes, and posterior reversible encephalopathy syndrome (PRES). Demographic variables between groups, including age, gender, education, and race/ethnicity collected upon enrollment will be compared to confirm equivalency and randomization. Primary and secondary usability and feasibility outcomes are summarized in Table 1. Each metric will be analyzed using paired t-tests to compare between groups and analysis of covariance to adjust for possible differences in demographics or initial assessments (baseline) between groups. Binary measures will entail chi-squared comparisons of proportions between groups. All data will be analyzed using the Statistical Package for Social Sciences software (SPSS, Inc. Chicago, IL). Statistical significance will be defined as  $p \leq 0.05$ .

**Table 2.** Usability and Feasibility Outcomes

Usability and Feasibility Outcomes	Estimated Percentage Usability or Feasibility
Determine the feasibility of retaining 18 patients in the protocol from enrollment to hospital discharge or three weeks (whichever comes first).	66%
Determine the patient satisfaction rate in the final cohort.	80%

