## **10.3 Milestones and Success Criteria:**

**PRIMARY:** Retention rate in protocol from enrollment to hospital discharge or three weeks (whichever comes first) of over 66%.

**SECONDARY:** Patient satisfaction rate with avatar in the final cohort of 80%; rate of completion of 80% of the HCT educational modules of 75%; rate of completion of post- pilot survey within 1 week of discharge of 90%.

**10.4 Risk Mitigation and Alternative Strategies:** After each group of 5 we will assess patient feedback and modify the avatar program; this iterative design will allow for rapid protocol improvements to be deployed to new patients in subsequent cohorts to move towards achieving the success criteria above. In case outcomes are disappointing during the first cohort, we may switch to a more frequent iteration rate, in conjunction with the advice of our consulting biostatistician.

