**CONTINUE**

**POST-PILOT SURVEY**

**Technology Usability**

1. Regardless of prior choice, my ideal care.coach avatar is a:
  - a. Dog
  - b. Cat
  - c. Other Animal
  - d. Human
  
2. I find the avatar easy to use.
  - a. Likert Scale (Strongly Agree to Strongly Disagree) ("on a scale of 1 to 5")
  
3. What do you like best about the avatar?
  - a. Write-in
  
4. What did you like least about the avatar?
  - a. Write-in
  
5. I like the appearance of the avatar.
  - a. Likert Scale (Strongly Agree to Strongly Disagree)
  
6. I had difficulty waking the avatar.
  - a. Likert Scale (Strongly Agree to Strongly Disagree)
  
7. My conversation with the avatar was clear and understandable.
  - a. Likert Scale (Strongly Agree to Strongly Disagree)
  
8. I felt like I was speaking to a person while using the avatar.
  - a. Likert Scale (Strongly Agree to Strongly Disagree)
  
9. Roughly, what percentage of your (insert number) hospital days did you want to use the avatar?
  - a. Scale of percentages (by 10% intervals)
  
10. The avatar interacted with me an appropriate number of times per day to encourage healthy habits such as eating, drinking, medications, and physical activity.
  - a. Likert Scale (Strongly Agree to Strongly Disagree)
  
11. Did you ever turn off or use the cover for the avatar?
  - a. Yes/No
  
12. Did you feel like your privacy was impacted negatively by the presence of the avatar?
  - a. Yes/No

**PROTOCOL TITLE:** *Development and Piloting of Avatar-based Intervention to Support Patients Undergoing Stem Cell Transplantation*

13. I felt safer in the hospital because of the avatar.
  - a. Likert Scale (Strongly Agree to Strongly Disagree)
14. I would use the avatar again in the hospital.
  - a. Likert Scale (Strongly Agree to Strongly Disagree)
15. I would use the avatar at home after discharge if it were available.
  - a. Likert Scale (Strongly Agree to Strongly Disagree)
16. I would use the avatar before I was admitted to the hospital to prepare for my stay and treatment.
  - a. Likert Scale (Strongly Agree to Strongly Disagree)
17. Using the avatar was fun.
  - a. Likert Scale (Strongly Agree to Strongly Disagree)
18. Using the avatar was an enjoyable challenge.
  - a. Likert Scale (Strongly Agree to Strongly Disagree)
19. I would recommend the avatar to others.
  - a. Likert Scale (Strongly Agree to Strongly Disagree)

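### The primary retention criterion alone can be met by patients who stay enrolled but stop responding to the avatar, and the plan does not secure the data that would show it

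*Combined protocol and SAP*

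**What the plan says.** Section 1.2 sets the purpose of Aim 2: "We will assess the feasibility of the patient education and relational functions of the digital avatar". The design in 8.1 is a "Single-arm feasibility pilot, with 3 cohorts of 6 patients (18 total").

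The primary endpoint in 7.2 is "Retention rate in protocol from enrollment to hospital discharge or three weeks (whichever comes first"). Section 10.3 makes it a success criterion: "Retention rate in protocol from enrollment to hospital discharge or three weeks (whichever comes first) of over 66"%. Table 2 in 10.1 words it as "Determine the feasibility of retaining 18 patients in the protocol from enrollment to hospital discharge or three weeks (whichever comes first"), with 66% beside it. Section 10.3 then lists three secondary criteria: 80% satisfaction in the final cohort, 75% of patients completing 80% of the educational modules, and 90% survey completion.

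On the device, 8.2 says "When the avatar is visually sleeping, the audiovisual (AV) stream is offline". The avatar tries to start contact several times a day. It returns to sleep if the patient is absent, does not answer or asks for privacy. Section 11.0 provides for withdrawal at the patient's wish, and for withdrawal by the investigators when a patient cannot use the device.

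On data, 9.2 says "We will collect data on feasibility outcomes (retention, satisfaction, completion of modules) via post-pilot survey". Section 6.0 says engagement data will be analyzed after each cohort. Section 9.4 says the vendor's meta-data stay with the vendor.

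**The concern.** Retained is not defined anywhere. A patient can stop using a bedside tablet without asking to leave the study, simply by no longer answering it. The primary endpoint as worded cannot separate that patient from one who used the avatar daily until discharge. Of the secondary criteria, module completion depends on use, but it does not show use continuing to discharge, and 10.3 does not say how it combines with the primary.

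At stake is what a retention rate above 66% would mean. Sections 9.2 and 12.0 (Potential Benefits) look ahead to a Phase 2 study and a randomized trial. A figure that shows only who stayed enrolled could be read there as evidence that inpatients kept using the intervention.

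**Working it through.** **The plan's own figure.** The sample size in 10.2 rests on accrual: 162 × 0.33 = 53.5 (stated as 54), and 54 × 0.33 = 17.8 (stated as 18). It reproduces. The plan gives no null rate, alpha or power for the retention criterion, so there is no power figure to check.

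**Pass mark.** 11/18 = 61.1% fails and 12/18 = 66.7% passes. Each patient is worth 1/18 = 5.6 percentage points. The exact 95% interval for 12/18 is 41% to 87%.

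**Does any rule link retention to use?**
- 7.2, Table 2 and 10.3 set no minimum number of interactions, days or minutes.
- 8.2 sends the avatar back to sleep after non-response, with no consequence for study status.
- 11.0 covers inability to use the device, not disuse.
- Table 1 in 8.5 schedules research-assistant check-ins at Day 5 and just before discharge, but names no use measure at either.

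So, read literally, all 12 patients needed for a pass could be non-users.

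**What the module criterion adds.** 0.75 × 18 = 13.5, so 14 completers are needed and at most 4 of 18 could be non-users. If the denominator were 12 retained patients, 0.75 × 12 = 9 would be needed. The plan does not state the denominator. Either way, zero use could not meet this criterion.

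**Size, by illustration.** The documents give neither a true retention rate r nor the share u of retained patients still using the avatar, so both are assumed. The probability of passing is P(X ≥ 12) for X ~ Binomial(18, p). Under the current wording p = r. For a retained-and-using rate p = r × u.

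| r | u | r × u | P(pass), current wording | P(at least 12 of 18 retained and using) |
|---|---|---|---|---|
| 0.80 | 1.00 | 0.80 | 0.949 | 0.949 |
| 0.80 | 0.90 | 0.72 | 0.949 | 0.783 |
| 0.80 | 0.80 | 0.64 | 0.949 | 0.513 |
| 0.80 | 0.75 | 0.60 | 0.949 | 0.374 |
| 0.90 | 0.90 | 0.81 | 0.999 | 0.960 |

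The fourth column does not move with u.

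**Could the collected data show disuse?**
- The survey named in 9.2 has no item in Appendix A that records retention or modules completed. Q9 asks on what share of hospital days the patient wanted the avatar, and Q11 asks "Did you ever turn off or use the cover for the avatar"; neither supplies the endpoint.
- The survey is given only after disenrollment, and its own target allows non-response: 0.90 × 18 = 16.2, so 17 returns meet it and one patient may have no survey.
- 6.0 needs engagement data that 9.4 says the site will not receive.

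**The case against.** The strongest reply is that 10.3 lists four criteria, not one, and that completing 80% of the modules takes substantial interaction. A reader might infer that the study as a whole can be declared successful with no use of the avatar. The documents do not support that: the module criterion cannot be met without use, and nothing says the primary decides alone. What stands is narrower. The primary alone is blind to use, and the plan is silent on how the criteria combine.

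A reader might also picture a device left asleep or covered for three weeks. Section 8.2 has the avatar wake itself several times a day, and it describes the cover as one for the camera, so covering it is a privacy choice and not proof of non-use. The route that remains is unanswered prompts. Likewise, no passage states that a non-user counts as retained; that follows from the absence of a definition.

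Use and the relational function are not ignored. Engagement is to be analyzed after each cohort, and survey items Q9, Q30 and Q31 touch on wish to use, unprompted use and loneliness. Keeping retention separate from engagement is a legitimate choice in an 18-patient pilot. Building a use rule into the primary while keeping a 66% mark set for a different quantity would be debatable. For that reason the remedy leaves the primary as it is.

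Finally, the documents offer no evidence that silent non-use will be common. The only engagement figure they give, an average of 61 minutes per patient per day in the earlier inpatient pilot, comes from a different population with shorter stays and does not suggest it.

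**Conclusion.** The point holds in limited form. The primary success criterion, at least 12 of 18 retained, can be met by patients who never withdraw but stop responding, and 10.3 does not require the use-dependent module criterion alongside it. The sources named for retention and module completion cannot yield either, and 6.0 and 9.4 conflict on engagement data; this second part needs no assumption.

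The fall in pass probability from 0.95 to 0.78 or 0.51 rests on assumed rates of 80% retention and 10% or 20% disuse, and on independent patients with a common rate. It shows sensitivity and does not predict a bias. A reader might infer that the retention figure will be inflated, or that a decision on a later trial hangs on it; the documents establish neither.

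**What to change.** - **7.2, Table 2 and 10.3:** define retained as still enrolled at discharge or three weeks, whichever is earlier, and keep this enrolled-only rate as the primary. Take it from the enrollment and disenrollment record for all 18 patients.
- **Beside the primary:** report a retained-and-using rate with all 18 as denominator. The sponsor should fix the minimum-use rule before cohort 1. The documents offer no basis for a particular rule, so none is proposed here.
- **9.2:** remove the survey as the source of retention and module completion. Take use and modules completed from a coded per-patient count keyed to study number.
- **9.4:** allow that coded count to reach the site, so that the analysis planned in 6.0 can be done.
- **10.3:** state the denominator for module completion, and state that feasibility will not be concluded from retention alone if that criterion is missed.

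The cost is wording in these sections, a small data-sharing amendment, a coded count from the vendor, and possibly a less favourable feasibility figure. No extra patients or visits are needed.
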